Participants will complete this task in each intervention condition (Audéo P90 + Roger On, Audéo P90 alone) and in each listening condition (-5, 0, and +5 dB SNR).

Speech intelligibility in noise will be completed following hearing aid fitting and REM.

9 Statistical design and analysis

Determination of Sample Size

In a previous investigation of Roger technology (Thibodeau, 2019), significant benefit of Roger, compared to hearing aids alone, was observed for speech intelligibility performance in a cohort of 10 adults. Thus, 10 adults will be recruited to participate in this clinical investigation. Additional participants may be recruited if preliminary results of speech intelligibility reveal higher intersubject variability than observed in previous studies, or if participants withdraw or must be excluded.

Statistical criteria of termination of trial

No *a priori* statistical criteria will be used to determine the termination of the trial. However, the trial may be terminated prior to the completion of all planned data collection if a statistically significant effect of the intervention is observed and no additional participants are able to be recruited.

Planned Analyses

The statistical analysis plan includes the methods and types of the analysis, the variables the data sets and the timeframe when the (interim) analysis is planned.

Datasets to be analyzed, analysis population

Speech intelligibility in noise performance will be recorded in proportion of words correctly repeated within each intervention condition (Audéo P90 + Roger On, Audéo P90 alone) in each listening condition (-5, 0, +5 dB SNR) for each anonymized participant.

Primary Endpoint Analysis

Primary analysis of study data will be completed at the conclusion of the data collection period by a representative of the sponsor (study manager). The results of the speech intelligibility task will be subjected to multivariate analyses of variance (MANOVA) to examine main and interaction effects of intervention.

Secondary Endpoint Analysis

If main or interaction effects are observed on MANOVA, post hoc tests will be used to examine differences in mean speech intelligibility performance across intervention for each listening condition. These post hoc tests will be completed at the conclusion of the data collection period by a representative of the sponsor (study manager).

Interim Analysis

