Interim analysis (MANOVA) will be completed on a rolling basis by a representative of the sponsor (study manager). This will be done to monitor study results as participants are enrolled and tested to determine whether inclusion criteria should be adjusted to include more participants to ensure an adequately powered study.

Safety Analysis

All safety related events will be constantly monitored by the investigators and will immediately reported to the Principle Investigator and representative of the study sponsor (study manager). Evaluation of any SAE, SADE, or UADE will be conducted promptly by the study manager using Sonova's standard medical device referral protocol. Confirmed UADEs will be reported to the IRB within 10 days after receiving notice of the event. If it is determined that an event or effect presents an unreasonable risk to subjects, this study, or those parts of the study presenting that risk, will be terminated no later than 5 working days after the determination is made and no later than 15 working days after Sonova USA first received notice of the event.

A safety analysis of the relevant data will be completed at the conclusion of the data collection period.

Deviation(s) from the original statistical plan

Deviations to the statistical plan will be captured and reported in an update to this document, with justification.

Handling of missing data and drop-outs

Should participants withdraw from the study or be lost to follow up prior to completion of all study tasks and/or conditions, no effort will be made to compute what their performance would have been in the incomplete tasks/conditions. Rather, this will be treated as missing data. Drop-outs will not be replaced, however, additional participants may be recruited/enrolled, depending on availability of volunteers.

10 Investigation Duration

Total expected duration of the clinical investigation: 2 months

Expected duration of each participant's participation: ≤ 2 hours

11 Data Handling and Management

Case Report Forms (CRF)

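### The primary MANOVA is also run as a rolling interim analysis that steers recruitment and eligibility, with no alpha, look schedule, maximum N or adjustment, so the confirmatory false-positive rate cannot be stated in advance

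*Combined protocol and SAP*

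**What the plan says.** Section 4 calls the design confirmatory, and section 2 sets out to demonstrate an improvement over hearing aids alone. The rest is in section 9.

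- **Primary Endpoint Analysis.** The method is "multivariate analyses of variance (MANOVA) to examine main and interaction effects of intervention". On timing and analyst: "Primary analysis of study data will be completed at the conclusion of the data collection period by a representative of the sponsor (study manager"). The plan does not say which effect decides success.
- **Interim Analysis.** "Interim analysis (MANOVA) will be completed on a rolling basis by a representative of the sponsor (study manager"). The aim is "to determine whether inclusion criteria should be adjusted to include more participants to ensure an adequately powered study".
- **Determination of Sample Size.** Ten adults, by precedent from an earlier study of the technology. "Additional participants may be recruited if preliminary results of speech intelligibility reveal higher intersubject variability than observed in previous studies"; withdrawals and exclusions are further reasons. No figure is given for the variability seen before.
- **Statistical criteria of termination.** The paragraph first disclaims any pre-set statistical criterion, then allows early termination "if a statistically significant effect of the intervention is observed and no additional participants are able to be recruited".
- **Planned Analyses.** The plan is said to include "the timeframe when the (interim) analysis is planned". The only timing given later is that the looks are rolling.
- **Missing data and drop-outs.** "Drop-outs will not be replaced, however, additional participants may be recruited/enrolled, depending on availability of volunteers".

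Nowhere is there an alpha, a sidedness, a number of looks, a maximum sample size or an adjustment.

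**The concern.** The final test follows an unknown number of runs of the same test on accumulating data, and those runs inform whether recruitment goes on and who may enter. A MANOVA shows the size of the effect and its p-value, not only the variability. Nothing confines the decision to variability, and the variability trigger has no number that could be checked afterwards. The error rate of the final test depends on how the looks are used, and the plan leaves that open.

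A change of inclusion criteria made with outcome data in view also changes the population being tested, which no adjustment of alpha repairs. Recording deviations and amendments with a justification, as sections 9 and 12 promise, makes such changes visible but does not control error.

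**Working it through.** **The plan's own figure.** N = 10 is the only design number, and it cannot be reproduced, because no alpha, power, effect size or SD accompanies it. For orientation, an exact paired t-test at an assumed two-sided 5% with n = 10 has 80% power at a standardised paired effect of 1.00 and 90% at 1.15.

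**Inputs from the documents.** Each participant is tested in both interventions at three SNRs; N = 10, extendable without a cap; the same MANOVA is used at interim and at the end.

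**Assumptions.** Two-sided 5%; normally distributed differences; complete data; no true effect. The caps (15, 20, 30) and the earliest look (n = 5) are illustrations.

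**Test.** Let D be a participant's mean difference over the three SNRs (with the device minus without). The main effect of intervention is t = mean(D) / (SD(D)/√n), with F(1, n−1) = t². Under normality its null distribution does not depend on the correlation between SNRs. Each rule was simulated in three sets of 400,000 null trials. A false claim of benefit is half the two-sided rate, by symmetry.

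| Rule | Two-sided error | False benefit |
|---|---|---|
| *Close to the text* | | |
| One test at n = 10, or recruitment ends for reasons unrelated to results | 5.0% | 2.5% |
| Extend 10 to 15 on SD only, threshold 0.9-1.2 × true SD | 5.1-5.7% | 2.5-2.9% |
| Extend 10 to 15 if observed power is below 80% (observed standardised effect below 1.00) | 5.4-5.5% | 2.7-2.8% |
| *Looser: recruitment stalls at n = 5-9, significance ends the trial, otherwise it resumes to 10* | | |
| Stall in a quarter of trials | 5.7% | 2.8-2.9% |
| Stall in half | 6.3-6.4% | 3.2% |
| Stall in all | 7.7-7.8% | 3.8-3.9% |
| *Not written, not excluded: extension because of non-significance* | | |
| 10, then 15 | 7.8-7.9% | 3.9-4.0% |
| One at a time, 10 to 15 | 10.2-10.4% | 5.1-5.2% |
| One at a time, 10 to 20 | 13.3-13.5% | 6.7% |
| One at a time, 10 to 30 | 17.4-17.5% | 8.7-8.8% |

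Stopping at the first significant look is not the written rule. For scale, from n = 5 it would give 12.5-12.6% (to 10), 16.4-16.5% (to 15), 19.1-19.3% (to 20) and 22.8-23.0% (to 30).

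**Which effect counts.** With the interaction tested by Hotelling T² (200,000 trials at each of the correlations 0, 0.3 and 0.6), counting either the main effect or the interaction as success gives 9.7-9.9% at a single test at n = 10, and 15.3-15.5% for looks at 10 and 15 at 0.05 each.

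**Bias.** Even if early termination were possible in every trial, the benefit would be overstated by only 4.7%, 3.5% and 1.4% at standardised effects of 0.5, 1.0 and 1.5.

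**Levels that hold 5% for the main effect.** In 1,000,000 null trials, SD-only extension tested at 0.05 peaks at 5.80% (cap 15, threshold 0.8 × true SD) and 6.16% (cap 20). Tested at 0.042 with cap 15 it peaks at 4.89%; at 0.040 with cap 20, at 4.99%. Efficacy looks at 10 and 15, each at 0.031, give 5.0-5.1%.

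**The case against.** The written triggers for adding participants are variability, withdrawals, exclusions and power; none is significance. On those readings the error stays between 5.0% and 5.7%. Early termination needs two conditions together, and if nobody more can be recruited, enrolment ends whatever the p-value, which brings the rate back to 5.0%. The stalling rows need a further step that the plan does not spell out: a non-significant look is followed by wider eligibility, and recruitment resumes. The plan does not say who takes the recruitment decision, only that the study manager runs the analysis. A single site and an expected duration of 2 months limit how far enrolment could run.

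Most of this stands, and it is why the larger figures should not set the weight of the point. It does not close the gap. The tool named is the treatment-effect test rather than a look at the SD, and no threshold ties the decision to variability. Widening eligibility after a look is exactly the use the Interim Analysis paragraph provides for. The sentence disclaiming statistical stopping criteria sits beside one that makes significance part of a stopping condition, so the paragraph is inconsistent rather than reassuring. It does not name the interim MANOVA as the source of that significance; this is inferred, because no other efficacy test is planned before data collection ends.

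Which effect decides success is a separate question that would exist with no interim look. It belongs here because any error level depends on the answer.

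**Conclusion.** The concern holds, and the plan should be changed. A trial presented as confirmatory has no false-positive rate that can be given in advance. The likely inflation is modest on the written rules and becomes material only if decisions follow significance, at 7.8% to 17.5% for the extension rules illustrated. No firm upper limit can be given, because no maximum N is stated. Bias in the estimated benefit is small.

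These figures rest on an assumed two-sided 5% level, normal differences, complete data, and the main effect alone. The endpoint is a percentage bounded at 0 and 100 and n is small, so the calibrated levels are approximate; 0.040 with a cap of 20 has almost no margin.

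**What to change.** In section 9:

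1. Delete the rolling efficacy MANOVA from Interim Analysis and the significance condition from the termination paragraph.
2. State alpha and sidedness. Name the main effect of intervention as the single effect that decides success, with the interaction and the per-SNR post hoc tests as follow-up.
3. Test it once, at the end of data collection, at N = 10 or at a stated maximum.
4. If the size may be revisited, allow one look at n = 10 at the SD of the within-participant differences only (no means, no p-values), with a stated threshold and cap. Test at about 0.042 for a cap of 15, or about 0.040 for a cap of 20; these hold 5% for thresholds of 0.5 to 1.3 times the true SD.
5. Do not change inclusion criteria on outcome data.

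If the sponsor prefers to keep efficacy looks, fix their number and timing, set a maximum N and use an alpha-spending boundary. For scale, equal levels of about 0.031 at 10 and 15 participants hold 5% for the main effect. If the interaction also counted as success, that rule would give 9.9-10.0%, and none of the levels above would hold 5%.

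The cost is wording and the loss of a running view of efficacy; there is less analysis to do. At a standardised effect of 1.0, testing at 0.042 instead of 0.05 lowers power from 80% to 77% at n = 10, and from 95% to 94% at n = 15.

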The primary objective of this study is to demonstrate an improvement in speech intelligibility in noise with the use of a Phonak Roger On remote microphone system compared to the use of hearing aids alone for a group of adults with moderate to severe hearing loss. There is no secondary objective.

3 Description of the investigational device

The intended purpose of the investigational device (i.e., Roger On) in the proposed clinical investigation is to pick up the voice of a talker and send it directly to the listener's ears. There are four main use cases for Roger On: (1) table mode, in which the Roger On device is placed on a table to hear the voices of people sitting around the microphone; (2) pointing mode, in which the listener holds the microphone in the direction of the person they want to hear; (3) presenter mode, in which the microphone is hung from a lanyard around the neck of (or clipped to the lapel of) a distant talker; and (4) TV/multimedia mode, in which the microphone is connected to a television or another audio source and the output is streamed directly into the listener's ears. In the proposed clinical investigation, Roger On will be used only in table mode.

The intended purpose of the Audéo P hearing aids (compatible devices to the Roger On) is to amplify and transmit sound to the ear and thereby compensate for impaired hearing. In this clinical investigation, the primary endpoint will be assessed with the compatible devices alone (Audéo P90 alone) and with the investigational device paired with the compatible devices (Audéo P90 + Roger On). When worn alone, the compatible devices amplify inputs

to the hearing aid microphones and transmit sound to the ear and thereby compensate for impaired hearing. When paired with the investigational device, the compatible devices receive the input from the investigational device, combine it with the signal from the hearing aid microphones (using default gain settings and mixing ratio prescribed by Phonak Target software), and transmit this blended signal to the ear.

4 Design of the clinical investigation

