1. Hearing impaired adults (minimum age: 18 years) who are experienced hearing aid users
2. Hearing loss is symmetric (no more than a 15 dB difference between the right and left ears at three contiguous frequencies) and moderate to severe in degree (N3-N5 standard audiogram)
3. Good written and spoken English language skills
4. Healthy outer ear (confirmed by otoscopy)
5. Informed consent as documented by signature

Exclusion criteria for participant selection:

1. Contraindications to the medical device noted upon otoscopy (e.g., ear canal drainage)
2. Known hypersensitivity or allergy to materials of the investigational device or compatible device
3. Inability to produce reliable test results
4. Known psychological problems
5. Reported symptoms of vertigo and dizziness by participant

8 Measurements and procedures

Pure-tone audiometry

Pure-tone audiometry is the gold standard measurement for assessing a person's hearing status. This involves measuring the threshold of hearing (i.e., the lowest level of sound that can be detected at least 50% of the time) at the frequencies most important for understanding speech (.25-8kHz) and recording these thresholds on an audiogram. Bone conduction thresholds are measured using a bone oscillator, and provide information about the integrity of the cochlea (organ of permanent hearing) and retrocochlear pathway by bypassing the outer and middle ears. Air conduction thresholds are measured using headphones or insert earphones, and thus assess the entire auditory pathway.

In this investigation, study candidacy will be determined based on potential participants' audiograms from previous clinical appointments within the past one year prior to enrollment.

Real Ear Measurement (REM)

Real-Ear Measurement (REM) is a tool used to objectively measure the hearing instrument's frequency response in a participant's ear. In this clinical investigation, on-ear REM will be completed using the Verifit2.

First, the participant's hearing thresholds will be entered into the Verifit2 and the appropriate hearing aid fitting formula (DSL v5, NAL-NL1, NAL-NL2) will be selected. Based on these entries, the software will determine the appropriate amplification targets. In this clinical investigation, the fitting formula that the participant's current hearing aids have been fit to will be selected. For most participants, this is the NAL-NL2 formula, as this is the most common fitting protocol used in a clinical adult population.

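### Interim results may be used to widen the inclusion criteria, and nothing fixes the moderate-to-severe (N3-N5) criterion or keeps an analysis set limited to it

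*Combined protocol and SAP*

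**What the plan says.** Section 2 limits the objective to showing a benefit "for a group of adults with moderate to severe hearing loss. There is no secondary objective". Section 7 turns this into an audiogram criterion, N3-N5. It also requires symmetric loss, hearing-aid experience and good English, none of which the objective mentions.

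Section 9 sets the sample at 10 by reference to the cohort size of an earlier study. Under Determination of Sample Size, more people may be added without any mention of eligibility: "Additional participants may be recruited if preliminary results of speech intelligibility reveal higher intersubject variability than observed in previous studies", or if participants withdraw or are excluded. Under Interim Analysis, the MANOVA is repeated as participants are tested, by the sponsor's study manager, in order to "determine whether inclusion criteria should be adjusted to include more participants to ensure an adequately powered study".

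The paragraph on data sets and analysis population describes the scores recorded for every participant and defines no subset. The primary analysis is one MANOVA of the speech results, followed by post hoc comparisons at each listening condition if effects are found. Section 4 calls the design confirmatory and states that neither experimenters nor participants are blinded. Section 9 (on deviations from the statistical plan) and section 12 require changes to be recorded in the document with a justification.

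**The concern.** Adjusting inclusion criteria so that more people qualify can only mean widening them. The plan makes the running outcome comparison the basis for that decision, and it leaves open which criteria may move. One of them, degree of hearing loss, is what defines the population in the only objective.

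If that criterion were widened, the plan as written would put everyone into the same MANOVA. The result would describe a mixture whose make-up was settled during the trial, while the objective would still name moderate to severe loss. Benefit in percent correct depends on where a listener sits on the performance curve, so a mixture can show a different pattern over -5, 0 and +5 dB SNR from that of the stated population. This is a question of who is studied. It is separate from the error rate of repeated looks, and adjusting alpha would not resolve it.

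**Working it through.** **1. The plan's own figure.** The sample size of 10 rests on precedent. The documents give no alpha, power, effect size or SD, so it cannot be reproduced, and adequate power has no benchmark against which an interim result could be judged.

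**2. Which criteria matter.** Setting sections 2 and 7 side by side:

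| Section 7 criterion | Named in the objective? | Effect of relaxing it alone |
|---|---|---|
| Moderate to severe loss, N3-N5 | Yes | Sample can leave the stated population |
| Symmetric loss | No | Sample stays within it |
| Hearing-aid experience | No | Sample stays within it |
| English skills | No | Sample stays within it |

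The point therefore concerns the N3-N5 criterion only.

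**3. Share of the sample outside N3-N5 (no model needed).** With k people added to 10, the share is k/(10 + k):
- k = 2: 2/12 = 17%
- k = 5: 5/15 = 33%
- k = 10: 10/20 = 50%

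If mean benefit outside N3-N5 is r times that inside, pooled benefit is (10 + k·r)/(10 + k) times the N3-N5 benefit. With k = 5 this is 0.67, 0.83, 1.00 or 1.17 for r = 0, 0.5, 1 or 1.5. The documents do not give r, so the shift could go either way.

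**4. Illustration by SNR.** Every input here is an assumption; none comes from the documents. Proportion correct is p(s) = 1/(1 + exp(-4·b·(s - m))), where b is the slope at the 50% point and m is the SNR giving 50% correct with hearing aids alone. The device is taken to be worth 6 dB for everyone, so benefit = 100·[p(s + 6) - p(s)]. N3-N5 listeners have m = +5 dB and milder listeners m = -2 dB, a gap of 7 dB. Pooled benefit = (10 × N3-N5 + 5 × milder)/15.

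Worked example, N3-N5, b = 0.08, s = -5:
- p(1) = 1/(1 + exp(1.28)) = 0.218
- p(-5) = 1/(1 + exp(3.2)) = 0.039
- benefit = 17.8 points

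Benefit in percentage points (shifts and means computed before rounding):

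| Slope | Group | -5 dB | 0 dB | +5 dB | Mean of three |
|---|---|---|---|---|---|
| 8 points/dB | N3-N5 | 17.8 | 41.1 | 37.2 | 32.1 |
| | Milder | 44.6 | 27.3 | 8.1 | 26.7 |
| | Pooled 10:5 | 26.8 | 36.5 | 27.5 | 30.3 |
| | Shift | +8.9 | -4.6 | -9.7 | -1.8 |
| 5 points/dB | N3-N5 | 19.1 | 28.1 | 26.9 | 24.7 |
| | Milder | 29.1 | 23.3 | 12.9 | 21.8 |
| | Pooled 10:5 | 22.4 | 26.5 | 22.2 | 23.7 |
| | Shift | +3.3 | -1.6 | -4.7 | -1.0 |

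**5. Sensitivity to the gap.** With the milder group's 50% point at 0 dB (a gap of 5 dB), the shifts are +7.8, -1.3 and -7.8 at slope 8, and +3.0, -0.4 and -3.3 at slope 5. Their means are (7.8 - 1.3 - 7.8)/3 = -0.4 and (3.0 - 0.4 - 3.3)/3 = -0.2.

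**6. Reading.** The average over SNRs hardly moves because shifts of opposite sign cancel. The profile over SNR does move, and that profile is what the interaction term and the post hoc tests report.

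**The case against.** The clause is a contingency. It speaks of deciding whether to adjust, it may never be used, and if used it might touch only symmetry, experience or language. All of that stands, which is why the point is confined to N3-N5.

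Any change would have to be recorded and justified, so a wider population would be visible to a reader. That also stands, but a record neither limits what may be changed nor keeps an analysis of the stated population.

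Scarcity of volunteers is a fair reason to want flexibility. Section 9 foresees that no more participants may be found and makes extra enrolment depend on availability, at a single site over 2 months. One cannot say that wider criteria would never be needed to raise the number. Still, section 9 already allows extra recruitment without touching eligibility. If high variability is the trigger, a more mixed group could increase it.

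The strongest objection is that each person is tested both with and without the device. A mixed group therefore does not bias the within-person contrast, and in the illustration benefit stays positive at every SNR. This is right for the bare question of whether there is an improvement. It does not cover the size and pattern of benefit in the population that the objective names.

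A reader might infer that the population could be steered toward a larger benefit. The documents do not show this. In the illustration, adding milder listeners lowers the average and lowers two of the three SNRs, and no document gives the benefit in any group outside N3-N5.

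**Conclusion.** The gap is real but narrow. A plan described as confirmatory lets unblinded, accumulating outcome results inform a widening of eligibility. It neither fixes the one criterion that defines its only objective nor keeps an analysis limited to those who meet it.

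If N3-N5 were widened and 5 people were added to 10, one third of the sample would lie outside the stated population. That figure is arithmetic. The effect on benefit is illustrative only. With a 7 dB gap between groups, the average over SNRs moves by about 1 to 2 points and single SNRs by about 2 to 10 points; with a 5 dB gap both are smaller. The slope, gain and gap are all assumed.

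Two stronger conclusions are not supported. One is that any relaxation of section 7 would take the sample outside the objective's population. The other is that the result would be biased in a known direction. This is a cheap improvement, not a flaw that invalidates the trial.

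**What to change.** In section 9 (Interim Analysis), replace the clause on adjusting inclusion criteria with a statement that interim data may be used only to decide whether to recruit more participants who meet the section 7 hearing-loss criterion (N3-N5).

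In section 9 (analysis population), add one sentence: if the criteria are later amended under section 12, the primary analysis and conclusion use participants who meet the version 1 N3-N5 criterion, and any others are reported separately and descriptively. Participants admitted by relaxing only symmetry, experience or language need not be left out on this ground.

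The cost is one clause replaced and one sentence added. The downside is possibly slower recruitment at a single site with 2 months planned. The documents give no figure for the supply of volunteers, so the size of that delay cannot be stated.
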